4.2 Scientific Rationale for Study Design

The randomized, placebo-controlled, double-blind superiority design and the selected endpoints of the study are consistent with regulatory guidance and are considered appropriate for non-hospitalized adult participants with COVID-19 [Food and Drug Administration 2020] [European Commission 2020].

The primary outcome is assessed through Day 29 (for 28 days of follow-up from randomization) to allow for a sufficient duration to reliably assess the safety and effectiveness of a 5-day treatment course of MK-4482. This duration is considered appropriate to capture important clinically relevant efficacy endpoints (eg, hospitalization, death). A 28-day follow-up period also aligns with the ACTT-1 Study Group's evaluation of remdesivir for treatment of COVID-19 in hospitalized adults [Beigel, J. H., et al 2020].

4.2.1 Rationale for Endpoints

4.2.1.1 Efficacy Endpoints

4.2.1.1.1 Primary Clinical Endpoint

The primary endpoint selected in this study is hospitalization or death. All-cause hospitalization (≥ 24 hours of acute care in a hospital or similar acute care facility, including emergency rooms or facilities created to address hospitalization needs during the COVID-19 pandemic) or death is intended to demonstrate the efficacy of MK-4482 relative to placebo using a clinically meaningful aspect of the disease that is relevant to non-hospitalized patients with COVID-19. This endpoint combines key clinical outcomes of interest, aiming to demonstrate the efficacy of study intervention in reducing serious complications of COVID-19.

4.2.1.1.2 Secondary Endpoints

To further evaluate efficacy of MK-4482 administered to non-hospitalized participants, additional relevant endpoints were selected, which are based on signs/symptoms associated with COVID-19 infection and other aspects of clinical progression of disease that are expected to improve with effective antiviral therapy:

- Time to sustained resolution or improvement, and time to progression of each targeted self-reported sign/symptom attributable to COVID-19 (Section 9.6.1) as reported by the participant through Day 29.
- WHO 11-point ordinal outcome scale to assess COVID-19-associated symptom burden (severity and duration), hospitalization, and death through Day 29 (Appendix 8).

4.2.1.2 Safety Endpoints

Safety evaluations include AE collection, physical examinations (including vital signs), and laboratory tests (hematology and chemistry) performed per the SoA (Section 1.3). AEs will be evaluated and assessed according to the guidelines in Section 8.4 and Appendix 3. Participants may be asked to return for unscheduled visits to perform additional safety monitoring.

In preclinical studies, mild hematologic toxicity was noted on Day 7, which progressed to more severe pancytopenia after 14-21 days of continuous exposure at 0.4-fold the NHC exposure at the 800 mg Q12H human dose of MK-4482. These changes were fully reversible (Section 2.3). Based on available unblinded data from the clinical development program for MK-4482, no clinically significant abnormalities in hematological laboratory tests as a function of either dose or treatment have been observed. However, based on preclinical findings, participants in this study will be monitored for any signs of bone marrow toxicity, including monitoring of CBC and platelets after initiating study intervention.

In preclinical studies, elevated liver enzymes were noted in rats at 62-fold the NHC exposure at 800 mg Q12H and noted in dogs at 19-fold the NHC exposure at 800 mg Q12H. Based on available unblinded data from the clinical development program for MK-4482, no clinically significant abnormalities in liver parameters as a function of either dose or treatment were noted. However, elevated LFTs with a DILI pattern will be considered an ECI and closely monitored.

No test-article related pathology changes in the pancreas to indicate pancreatic toxicity were noted in nonclinical studies and lipase and amylase were not measured. Transient elevations of serum lipase were observed at least 3 days after last dose in the Phase 1 study; the incidence of these elevations was comparable between recipients of MK-4482 and placebo. The occurrence and magnitude of these elevations did not appear to be dose related, and they were not associated with abdominal/gastrointestinal symptoms. However, as asymptomatic lipase elevations and clinical pancreatitis have been associated with some nucleoside analogs, changes in amylase or lipase were considered an ECI and closely monitored in Part 1 of this

study and MK-4482-001. Based on available unblinded data from the clinical development program for MK-4482, no clinically significant abnormalities in amylase or lipase as a function of either dose or treatment were noted. Thus due to the lack of preclinical findings and no trend noted in MK-4482 studies to date, elevated amylase, or lipase $>3X$ the upper limit of normal is not considered an ECI for Part 2.

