8.4.7 Events of Clinical Interest

Selected serious and nonserious AEs are also known as ECIs and must be reported to the Sponsor.

Events of clinical interest for this study include:

1. An elevated AST or ALT lab value that is greater than or equal to 3X the upper limit of normal and an elevated total bilirubin lab value that is greater than or equal to 2X the upper limit of normal and, at the same time, an alkaline phosphatase lab value that is less than 2X the upper limit of normal, as determined by way of protocol-specified laboratory testing or unscheduled laboratory testing.*

*Note: These criteria are based upon available regulatory guidance documents. The purpose of the criteria is to specify a threshold of abnormal hepatic tests that may require an additional evaluation for an underlying etiology. The study site guidance for assessment and follow-up of these criteria can be found in the Investigator Study File Binder (or equivalent).

2. Any postbaseline platelet value <50,000/ μ L, as determined by protocol-specified and/or unscheduled laboratory testing.

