9.6.2 Statistical Methods for Safety Analyses

Safety and tolerability will be assessed by clinical review of all relevant parameters including AEs, laboratory values and vital signs.

The analysis of safety results will follow a tiered approach as shown in [Table 6](#). The tiers differ with respect to the analyses that will be performed. For this protocol, only ECIs are considered Tier 1 events. AEs (specific terms as well as system organ class terms) and events that meet PDLCs in laboratory values or vital signs will be classified as belonging to "Tier 2" or "Tier 3" based on the number of events observed.

Tier 1 Events

Safety parameters or AEs of special interest that are identified a priori constitute "Tier 1" safety endpoints that will be subject to inferential testing for statistical significance with p-values and 95% CIs to be provided for between-treatment differences in the proportion of participants with events; these analyses will be performed using the unstratified Miettinen and Nurminen method [Miettinen, O. 1985], an unconditional, asymptotic method. Since the stratification factors are not considered to be related to safety endpoints, they will not be included as stratification factors in the safety analyses.

Tier 2 Events

Tier 2 parameters will be assessed via point estimates with 95% CIs provided for differences in the proportion of participants with events (also via the Miettinen and Nurminen method [Miettinen, O. 1985]).

Membership in Tier 2 requires that at least 4 participants in at least one treatment group exhibit the event. The threshold of at least 4 events was chosen because the 95% CI for the between-group difference in percent incidence will always include zero when treatment groups of equal size each have less than 4 events and thus would add little to the interpretation of potentially meaningful differences. Because many 95% CIs may be provided without adjustment for multiplicity, the CIs should be regarded as a helpful descriptive measure to be used in review, not a formal method for assessing the statistical significance of the between-group differences in AEs and predefined limits of change.

In addition to individual events that occur in 4 or more participants in any treatment group, the broad AE categories consisting of the proportion of participants with any AE, a drug-related AE, a serious AE, an AE which is both drug-related and serious, and discontinuation due to an AE will be considered Tier 2 endpoints.

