Tier 3 Events

Safety endpoints that are not Tier 1 or 2 events are considered Tier 3 events. Only point estimates by treatment group are provided for Tier 3 safety parameters.

Continuous Safety Measures

For continuous measures such as changes from baseline in laboratory and vital signs parameters, summary statistics for baseline, on-treatment, and change from baseline values will be provided by treatment group in table format. In addition, summary statistics for the difference between treatment groups will also be provided.

Table 6 Analysis Strategy for Safety Parameters

Safety Tier	Safety Endpoint ^a	p-value	95% CI for Treatment Comparison	Descriptive Statistics
Tier 1	ECIs	X	X	X
Tier 2	Any AE		X	X
	Any Serious AE		X	X
	Any Drug-Related AE		X	X
	Any Serious and Drug-Related AE		X	X
	Discontinuation due to AE		X	X
	Discontinuation due to Drug-Related AE		X	X
	Specific AEs by SOCs and PT (incidence ≥ 4 participants in at least 1 of the treatment groups)		X	X
	PDLCs ^b (incidence ≥ 4 participants in at least 1 of the treatment groups)		X	X
Tier 3	Specific AEs by SOC and PT (incidence < 4 participants in each of the treatment groups)			X
	PDLCs ^b (incidence < 4 participants in each of the treatment groups)			X
	Change from Baseline Results (Labs, Vital Signs)			X

AE=adverse event; CI=confidence interval; ECI=event of clinical interest; PT=preferred term; SOC=system organ class; PDLC=pre-defined limit of change; X=results will be provided.

^a Adverse Event references refer to both Clinical and Laboratory AEs.

^b Includes only those endpoints not pre-specified as Tier 1 or not already pre-specified as Tier-2 endpoints.

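### Bone marrow toxicity is a named risk, but the only formally tested marrow outcome is platelets <50,000/µL, and changes in platelets, neutrophils and hemoglobin are to be reported without confidence intervals

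*Combined protocol and SAP*

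**What the plan says.** Section 4.2.1.2 describes the preclinical finding: "mild hematologic toxicity was noted on Day 7, which progressed to more severe pancytopenia after 14-21 days" of continuous exposure, at 0.4-fold the clinical exposure at 800 mg Q12H. It adds that the changes were fully reversible and that unblinded clinical data have shown no clinically significant hematology abnormality by dose or treatment. It still commits the study to watching for marrow toxicity: "participants in this study will be monitored for any signs of bone marrow toxicity, including monitoring of CBC and platelets after initiating study intervention".

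The safety analysis is tiered (Section 9.6.2, Table 6):

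- **Tier 1 (p-value and 95% CI).** "For this protocol, only ECIs are considered Tier 1 events". Section 8.4.7 lists two such events, a hepatic pattern and "Any postbaseline platelet value <50,000" per microliter.
- **Tier 2 (95% CI for a difference in proportions).** This covers specific adverse events, including laboratory ones (Table 6, footnote a), and predefined limits of change (PDLCs), when at least 4 participants in one group are affected. Section 9.4.2 grades PDLCs by criteria adapted from DAIDS, from the most abnormal value while on study intervention.
- **Tier 3.** "Only point estimates by treatment group are provided for Tier 3 safety parameters". Laboratory and vital-sign change from baseline sits here, with neither the p-value nor the CI column marked.

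The continuous-measures text in Section 9.6.2 also promises summary statistics for the difference between groups. It names no interval, model or visit. Central hematology is drawn on Day 1, Day 3, EOT, and Days 10, 15 and 29 (Section 1.3).

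**The concern.** The only marrow outcome with a formal test is an extreme one. Section 5.2 excludes anyone with platelets below 100,000/µL, so a participant who met that limit at screening must lose at least half of the count to qualify. Neutrophils and red cells, the rest of a pancytopenia, have no Tier 1 outcome.

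A short course with a modest marrow effect would show mainly as a shift in the distribution of counts, and that analysis has no stated precision. The Tier 2 PDLC interval does not fill the gap after dosing. Dosing ends on Days 5 to 7 (Section 8.1.8.1), so on a literal reading only the Day 3 and EOT draws count. The dog changes appeared at Day 7 and worsened from Day 14, although under continuous dosing (Section 4.3.1).

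At stake is what the final report can say. With about 850 participants per group and five post-baseline draws, it could state how large a mean fall is excluded. Nothing in the plan commits it to do so.

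**Working it through.** **Inputs.** 850 per group, two-sided 5% alpha, no multiplicity adjustment (Section 9.9.3). The tiers and the 4-participant rule come from Section 9.6.2. The documents give no SD for any blood count, so results are in SD units or under stated assumptions.

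**1. The plan's own figures reproduce.**
- Chance of at least one event at 1% incidence: 1 − 0.99^850 = 99.98% (plan: >99.9%).
- Upper bound with no events: 1 − 0.025^(1/850) = 0.433%, or 1 in 231 (plan: <0.44%, 1 in 231).
- Table 10: power for the six listed pairs is 90.5, 91.1, 90.8, 90.5, 90.6 and 90.1% (plan: about 90%).
- The 4-participant rule: the Miettinen-Nurminen score statistic is z = 1.73 for 3 vs 0 (p = 0.083) and z = 2.00 for 4 vs 0 (p = 0.045). The rule is sound.

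**2. What the Tier 1 platelet test can find.** With no placebo events, significance needs at least 4 events on MK-4482. Power is P(X ≥ 4) for X ~ Binomial(850, p):

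| True incidence | Expected events | Power |
|---|---|---|
| 0.2% | 1.7 | 9% |
| 0.5% | 4.25 | 61% |
| 0.65% | 5.5 | 80% |

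This is reasonable for a rare severe event. For a general shift in counts the test is weak, and how weak depends on the assumed distribution:
- Lognormal platelets, median 200–250 ×10⁹/L, log-SD 0.25–0.40: a 10% fall moves the share below 50 from at most 0.03% to at most 0.07%. Power is below 1%.
- Normal platelets, mean 180–260, SD 50–80: a 0.157 SD shift gives power of 3% to 37%, and 10% in the middle case (220, 65). The 37% case needs about 44 of 850 placebo participants below 50,000/µL (5.2%), which is hard to square with the entry limit.

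**3. What an interval on the mean difference can find.**
- CI half-width: 1.96 × √(2/850) = 0.095 SD.
- Shift with 80% power: (1.960 + 0.842) × √(2/850) = 0.136 SD.
- Shift with 90% power: (1.960 + 1.282) × √(2/850) = 0.157 SD.

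**4. Threshold outcomes for the same shifts** (normal approximation, rough below about 1% incidence). If a proportion p of placebo crosses a limit, a shift of d SD moves it to Φ(Φ⁻¹(p) + d). Power at 850 per group:

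| Placebo incidence | 0.157 SD | 0.3 SD | 0.5 SD |
|---|---|---|---|
| 0.1% | 6% | 12% | 31% |
| 1% | 15% | 47% | 92% |
| 5% | 36% | 89% | >99% |
| 10% | 50% | 97% | >99% |

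The PDLC route therefore picks up large shifts well and small ones poorly. The SD here is that of the count itself. The ANCOVA residual SD is no larger, so the contrast with step 3 is not exaggerated.

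**5. In percent, under assumed SDs.** Allow 800 evaluable per group and work on log counts. The fall with 90% power is 1 − exp(−3.242 × s × √(2/800)) = 1 − exp(−0.162 s).
- Platelets, s = 0.15 to 0.30: 2.4% to 4.7%.
- Neutrophils, s = 0.3 to 0.6: about 5% to 9%.

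**The case against.** The plan does more than the Tier 1 list suggests.

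- **A between-group summary of continuous laboratory values is planned.** A shift would be displayed. If the summaries carry N and SD, as Section 9.12 specifies for exposure, a reader could derive an unadjusted interval.
- **Tier 2 covers graded limits and laboratory adverse events.** Adverse events are collected to 14 days after dosing, about Days 19 to 21, so a clinically significant fall at Day 10 or 15 can reach a Tier 2 interval.
- **Section 4.2.1.2 promises monitoring, not inference.** Repeated central hematology, investigator review, a platelet stopping criterion, the platelet event of clinical interest and periodic eDMC review deliver it.
- **The human data are reassuring.** Severe pancytopenia in animals followed 14 to 21 days of continuous exposure and reversed. Treatment here lasts 5 days.
- **More intervals bring chance findings.** Three counts at five draws give 15. If they were independent, 1 − 0.95^15 = 54% is the chance that at least one excludes no effect.

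Most of this stands. It rules out three stronger inferences a reader might draw: that a real shift would go undetected, that the Tier 1 test could find nothing, and that a monitoring commitment is broken. It does not supply a bound. The Tier 2 routes are threshold-based or depend on investigator judgment. The PDLC list is not itemized, and adverse event collection ends before Day 29. The continuous-measures text also speaks of on-treatment values, without saying whether Days 10, 15 and 29 are included.

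**Conclusion.** The point holds as a gap in reported precision, not in detection. Platelets <50,000/µL is the only marrow outcome with a formal test, and no interval is specified for change in platelets, neutrophils or hemoglobin. A 0.5 SD shift would probably be visible in a PDLC interval where placebo incidence is 1% or more (power 92% or higher). A shift near 0.157 SD would usually appear only as a point estimate, although an interval on the mean difference has 90% power for it. The plan therefore does not equip the report to state how large a fall is excluded, particularly at Days 10, 15 and 29.

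The SD-unit results rest on normal approximations and 850 per group. The percentage falls rest on assumed SDs, and nothing in the documents says what size of fall matters clinically. Nor do the documents show a marrow signal in humans or predict a delayed fall after 5 days of dosing, because the dog timing comes from continuous dosing. This is a worthwhile, inexpensive improvement and does not invalidate the safety analysis.

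**What to change.** In the continuous-measures text of Section 9.6.2 and the change-from-baseline row of Table 6, add an analysis of platelets, absolute neutrophil count and hemoglobin. At each scheduled post-baseline draw (Day 3, EOT, Days 10, 15 and 29), report the between-group difference as a ratio on log counts, with a 95% CI from an ANCOVA on the Day 1 value.

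Put the change there and not in Tier 2, which is defined for differences in proportions. Leave the event-of-clinical-interest, PDLC and adverse event tiers unchanged.

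The cost is SAP wording and three model tables from data already collected, with no new visits, samples or alpha. The downside is about 15 unadjusted intervals, of which 15 × 0.05 = 0.75 would be expected to exclude no effect by chance if there were none. Label them descriptive, as Section 9.6.2 already does for Tier 2 intervals.

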4.2.1.3 Pharmacokinetic Endpoints

Blood samples for PK assessment and concentrations of the MK-4482 nucleoside and triphosphate will be collected from all participants as described in the SoA (Section 1.3) and Section 8.6. As appropriate, PK-efficacy and PK-AE relationships for MK-4482 will also be evaluated. In Part 1, PBMC PK parameters (eg, C_{trough}) will be estimated. In Part 2, plasma PK parameters (eg, C_{trough}) will be summarized and in Parts 1 and 2, PK plasma parameters will be measured. PBMC PK samples will be used to evaluate the concentration of intracellular NHC-triphosphate, the active moiety resulting from dosing of MK-4482. Intracellular PBMC concentrations can help explain the relationship between MK-4482 dose and efficacy and safety.

4.2.1.4 Virology Endpoints

The study will evaluate SARS-CoV-2 RNA and infectious virus to assess the impact of MK-4482 on various aspects of SARS-CoV-2 viral dynamics.

Reducing SARS-CoV-2 VL and eradicating the virus are essential to recovery and has important implications for transmission and infection control strategies. The mechanism of antiviral activity of MK-4482 is viral error catastrophe predicated on increasing the viral mutation rate beyond a biologically-tolerable threshold resulting in impairment of viral fitness leading to viral elimination. These endpoints are aimed at assessing the antiviral activity of MK-4482 as well as evaluating the rate of viral mutagenesis with respect to MK-4482 treatment.

4.2.1.5 Future Biomedical Research

The Sponsor may provide samples, as described in Section 8.9, for which consent was provided during this study, to researchers including additional third parties (eg, a university investigator).

Such research is to address emergent questions not described in the protocol and will only be conducted on specimens as described in Section 8.9. Specimens will only be provided from appropriately consented participants. The objective of providing the specimens for FBR is to explore and identify biomarkers that inform the scientific understanding of diseases and/or their therapeutic treatments. The overarching goal is to use such information to develop safer, more effective drugs/vaccines, and/or to ensure that participants receive the correct dose of the correct drug/vaccine at the correct time. The details of FBR research are presented in Appendix 6.

4.2.2 Rationale for the Use of Comparator/Placebo

This study will be placebo-controlled in order to avoid bias in the collection/evaluation of data during study conduct and to assess whether any observed effects are treatment-related or an impact of study participation. Participants may receive Sponsor-designated standard of care treatment (Section 6.5), as appropriate, in addition to study intervention (MK-4482 or matching placebo).

There are currently no orally available direct-acting antivirals approved for the treatment of COVID-19 to serve as an active comparator, therefore placebo will be used.

4.2.3 Rationale for the Selected Participant Population

The rationale for the participant population selected for this study is as follows:

- **Participants with mild and moderate COVID-19:** Participants with mild and moderate COVID-19 (Appendix 9) are typically managed outside of the hospital and may benefit from administration of MK-4482 [Food and Drug Administration 2020]. Participants with severe and critical COVID-19 at randomization are excluded because they are expected to require hospitalization and would be out of scope for this study.
- **Participants at increased risk for severe illness from COVID-19:** Certain characteristics or underlying medical conditions (Appendix 10) have been identified that place patients at increased risk for severe illness from COVID-19, which may result in hospitalization, ICU-level care, ventilatory support, or death. This study focuses on higher risk non-hospitalized participants who may benefit from MK-4482, aiming to reduce the number of participants who develop severe illness from COVID-19 and need to be hospitalized or die. Thus, all participants must have at least 1 characteristic or underlying medical condition associated with being at increased risk for severe illness from COVID-19 to ensure the drug is being evaluated in the non-hospitalized population at higher risk.
- **Participants with signs/symptoms attributable to COVID-19 for ≤ 5 days:** Eligible participants must have COVID-19 signs/symptoms onset no more than 5 days prior to randomization. SARS-CoV-2 VLs are highest early in the course of disease, present 1-2 days prior to symptom onset, and persist for 7-12 days in moderate cases and up to 2 weeks in severe cases [Cevik, M., et al 2020]. Based on the viral kinetics of SARS-CoV-2 and the mechanism of action of MK-4482 (inhibition of viral replication), study participants must have signs/symptoms attributable to COVID-19 for ≤ 5 days prior to randomization; all efforts should be made to administer the first dose on Day 1 (randomization), but administration of the first dose must occur within 24 hours of randomization. Furthermore, as the host inflammatory response predominates during later stages of disease as COVID-19 progresses, treatment with antiviral therapy is likely to have a greater benefit with early treatment rather than delayed treatment >5 days after signs/symptoms onset, especially in the non-

hospitalized setting wherein patients are often earlier in the course of their disease and intervention can occur sooner than in the hospital setting.

